# **Assessment of Causality**

- The investigator is obligated to assess the relationship between trial treatment/trial procedure and each occurrence of each AE/SAE.
- The investigator will use clinical judgment to determine the relationship.
- Alternative causes, such as underlying disease(s), concomitant therapy, and other risk factors, as well as the temporal relationship of the event to trial treatment administration will be considered and investigated.
- The following table can be taken as guidance:

Causality Term	Assessment Criteria	Assessed as
Certain	
 
Event or laboratory test abnormality, with plausible time relationship to drug intake
 
Cannot be explained by disease or other drugs
 
Response to withdrawal plausible (pharmacologically, pathologically)
 
	Related

CONFIDENTIAL Page 102 of 122

\* Generally, an AE is defined as recovered/resolved if all symptoms have ceased, no medication for treatment of the event is taken anymore and no other measures (e.g., hospitalization) are ongoing.

	
 
Event definitive pharmacologically or phenomenologically (i.e., an objective and specific medical disorder or a recognized pharmacological phenomenon)
 
Rechallenge satisfactory, if necessary
 
	
Probable/ Likely	
 
Event or laboratory test abnormality, with reasonable time relationship to drug intake
 
Unlikely to be attributed to disease or other drugs
 
Response to withdrawal clinically reasonable
 
Rechallenge not required
 
	Related
Possible	
 
Event or laboratory test abnormality, with reasonable time relationship to drug intake
 
Could also be explained by disease or other drugs
 
Information on drug withdrawal may be lacking or unclear
 
	Related
Unlikely	
 
Event or laboratory test abnormality, with a time to drug intake that makes a relationship improbable (but not impossible)
 
Disease or other drugs provide plausible explanations
 
	Not related

It is sufficient to document the causality in the source data and eCRF as:

- Related, or
- Not related.

For an event considered "related to trial treatment" there is a **reasonable possibility** of a causal relationship.

For an event considered "not related to trial treatment" there is **no reasonable possibility** of a causal relationship.

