7 ANALYSIS SETS AND SUBGROUPS

7.1 Analysis sets

The following analysis sets are defined:

Population	Description
Screened	The screened analysis set is defined as all patients who sign the informed consent form (ICF).
Intent-to-Treat (ITT)	Part 1: The ITT set is defined as all patients to whom IMP is assigned. Part 2: The ITT set is defined as all patients who are randomized to the IMP.
Modified Intent-to-Treat (mITT)	Part 1: The mITT set is defined as all patients to whom IMP is assigned and have a baseline and at least one post-baseline (i.e., one on-treatment or post-treatment) tumor assessment (clinical or imaging assessment). Part 2: The mITT set is defined as all patients who are randomized to the IMP and have a baseline and at least one post-baseline (i.e., one on-treatment or post-treatment) tumor assessment (clinical or imaging assessment).
Safety (SAF)	The safety set is defined as all patients who have received IMP (i.e., at least 1 dose of W_pro1 and/or cemiplimab).
DLT Evaluation	Only applicable for Part 1: The DLT evaluation set includes all patients from the safety set who either have completed the DLT evaluation period and meet the minimum exposure criterion or have experienced a DLT during C1. Patients who do not experience any DLTs during C1 are considered to be evaluable if they have been observed for a minimum of 21 days following the first dose and are considered to have sufficient safety data to conclude that a DLT did not occur. A patient is considered to have met the minimum exposure criterion if the relative dose intensity of W_pro1 in C1 is at least 90%.
Per Protocol (PP)	The per protocol (PP) set is defined as all patients who have received IMP and fulfil the following criteria: 
 • The absence of any important protocol deviations that could affect the primary efficacy analysis • The completion of a minimal exposure to the treatment of 1 cycle • Availability of baseline and at least one on-treatment / post-treatment tumor assessment Important deviations will lead to an exclusion of patients from the PP set and will be agreed at the data review meeting (DRM) prior to database snapshot for the final analysis. Protocol deviations that may be considered important will be specified in the SAP (see Section 7.2)

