8.9 Safety analyses

Safety data that will be summarized include extent of exposure, AEs, occurrence of DLTs during Part 1, clinical laboratory assessments, vital signs and body weight, ECGs, physical examination and ECOG performance status (ECOG PS). All safety analyses will be based on the safety set and will be summarized by treatment groups, and for several combined treatment groups as defined in Section 13.4, unless otherwise stated.

Patients will be assigned to the treatment groups according to the actual treatment they have received (“as treated”).

All safety data will be listed for the safety set.

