8.9.3 Adverse events

AEs will be coded using the MedDRA® (version 22.1 or later version) coding system to get a SOC and PT for each AE and will be graded for severity using NCI CTCAE v5.0.

A **TEAE** is defined as any AE with an onset date on or after the first administration of IMP (if the AE was absent before the first administration of IMP (W_pro1 or cemiplimab, whichever comes first)) or worsened after the first administration of IMP (if the AE was present before the first administration of IMP).

AEs with an onset date more than 30 days (after the last administration of W_pro1) or 90 days (90 days after last administration of cemiplimab for Part 2, Arm 1A and Arm 2), respectively, after the last administration of W_pro1 or cemiplimab will be considered as treatment-emergent only if assessed as related to IMP by the investigator. TEAEs will be summarized overall and by treatment group for patients in the safety set.

For patients from Arm 1B who switch to cemiplimab monotherapy, the analysis of AEs will be additionally performed for each IMP separately, (i.e. only TEAEs from the first dose of W_pro1 until last dose of W_pro1 +30 days will be reported as TEAEs for Arm 1B).

In addition, **cemiplimab TEAEs** will be reported in separate AE tables using the subsequent cemiplimab monotherapy on progression set. Cemiplimab TEAEs are defined as TEAEs with an onset date on or after the first dose of cemiplimab until the last dose of cemiplimab +90 days. TEAEs with an onset within the 30 days after last dose of W_pro1 but after start of first cemiplimab treatment will be counted twice, as TEAE for Arm 1B and as cemiplimab TEAE in the respective tables and listings.

AEs started prior to first administration of IMP or AEs after last administration of IMP (follow-up AEs) will be included only in the AE listings.

AEs related to W_pro1

AEs related to W_pro1 are AEs with the item "Causality (relationship to W_pro1)" ticked "*Related*" in "*Adverse Events*" form of the eCRF. If the item is missing, the AE will be considered as related to W_pro1.

AEs related to cemiplimab

AEs related to cemiplimab are AEs with the item "Causality (relationship to cemiplimab)" ticked "*Related*" in "*Adverse Events*" form of the eCRF. If the item is missing, the AE will be considered as related to cemiplimab.

AEs related to IMP (W_pro1 + cemiplimab)

AEs related to IMP are AEs related to either W_pro1 or cemiplimab (or both).

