The number and percentage of patients for each category above will be summarized by SOC and PT as per MedDRA. If a SOC / PT is reported more than once for a patient, the patient will only be counted once for this SOC / PT. All AE summary tables will be sorted by descending frequency (%) by SOC and by PT within SOC with respect to the Parts 1 and 2 Total column. The number of events will be summarized in the same table.

The following AE tables by SOC and PT will be generated:

- TEAEs by System Organ Class and Preferred Term
- TEAEs related to IMP by System Organ Class and Preferred Term
- TEAEs related to W_pro1 by System Organ Class and Preferred Term

- TEAEs related to Cemiplimab by System Organ Class and Preferred Term
- Grade ≥ 3 (Maximum intensity) TEAEs by System Organ Class and Preferred Term
- Grade ≥ 3 TEAEs related to IMP by System Organ Class and Preferred Term
- Grade ≥ 3 TEAEs related to W_pro1 by System Organ Class and Preferred Term
- Grade ≥ 3 TEAEs related to Cemiplimab by System Organ Class and Preferred Term
- TEAEs related to trial procedure by System Organ Class and Preferred Term
- TEAEs related to prostate cancer surgery (Part 2 Arm 2 / Arm 3) by System Organ Class and Preferred Term
- Any Serious TEAEs by System Organ Class and Preferred Term
- Serious TEAEs related to IMP by System Organ Class and Preferred Term
- Serious TEAEs related to W_pro1 by System Organ Class and Preferred Term
- Serious TEAEs related to Cemiplimab by System Organ Class and Preferred Term
- Serious TEAEs leading to death by System Organ Class and Preferred Term
- Serious TEAEs leading to death related to IMP by System Organ Class and Preferred Term
- Serious TEAEs leading to death related to W_pro1 by System Organ Class and Preferred Term
- Serious TEAEs leading to death related to Cemiplimab by System Organ Class and Preferred Term
- TEAEs leading to IMP dose reduction by System Organ Class and Preferred Term
- TEAEs leading to W_pro1 dose reduction by System Organ Class and Preferred Term
- TEAEs leading to Cemiplimab dose reduction by System Organ Class and Preferred Term
- TEAEs leading to IMP dose delay by System Organ Class and Preferred Term
- TEAEs leading to W_pro1 dose delay by System Organ Class and Preferred Term
- TEAEs leading to Cemiplimab dose delay by System Organ Class and Preferred Term
- TEAEs leading to IMP dose modification by System Organ Class and Preferred Term

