	14.2.4.1.7a	Progression-free Survival (PFS) based on PCWG3, SAS output	Cemi Mono on PD set	
Figure	14.2.4.1.8	Kaplan-Meier curve for Progression-free Survival (PFS) based on PCWG3	Cemi Mono on PD set	
	14.2.4.1.9	Progression-free Survival (PFS) based on iRECIST (central reading)	Cemi Mono on PD set	
	14.2.4.1.9a	Progression-free Survival (PFS) based on iRECIST (central reading), SAS output	Cemi Mono on PD set	
Figure	14.2.4.1.10	Kaplan-Meier curve for Progression-free Survival (PFS) based on iRECIST (central reading)	Cemi Mono on PD set	
	14.2.4.1.11	Progression-free Survival 2 (PFS2) based on PCWG3	Cemi Mono on PD set	
	14.2.4.1.11a	Progression-free Survival 2 (PFS2) based on PCWG3, SAS output	Cemi Mono on PD set	
Figure	14.2.4.1.12	Kaplan-Meier curve for Progression-free Survival 2 (PFS2) based on PCWG3	Cemi Mono on PD set	
	14.2.4.1.13	Overall Survival (OS)	Cemi Mono on PD set	
	14.2.4.1.13a	Overall Survival (OS) SAS output	Cemi Mono on PD set	
Figure	14.2.4.1.14	Kaplan-Meier curve for Overall Survival (OS)	Cemi Mono on PD set	
14.2.5		Further Efficacy Analyses		
	14.2.5.1.1	Disease status during Survival Follow-up Period	mITT set	
	14.2.5.1.2	Biochemical recurrence after radical prostatectomy – post-treatment PSA values	mITT set	
	14.2.5.1.3	Time from treatment start to post-treatment prostatectomy – LPC patients	mITT set	
14.3		Safety Data		
14.3.1		Displays of Adverse Events		
	14.3.1.1	Summary of adverse events	Safety set	Yes
	14.3.1.2	Number (%) of patients with TEAEs by system organ class and preferred term	Safety set	Yes
	14.3.1.3	Number (%) of patients with TEAEs related to IMP by system organ class and preferred term	Safety set	Yes
	14.3.1.4	Number (%) of patients with TEAEs related to W_pro1 by system organ class and preferred term	Safety set	

Header	Table Number	Name	Analysis Set	Interim Analysis
	14.3.1.5	Number (%) of patients with TEAEs related to Cemiplimab by system organ class and preferred term	Safety set	
	14.3.1.6	Number (%) of patients with maximum intensity grade ≥ 3 TEAEs by system organ class and preferred term	Safety set	Yes
	14.3.1.7	Number (%) of patients with maximum intensity grade ≥ 3 TEAEs related to IMP by system organ class and preferred term	Safety set	Yes
	14.3.1.8	Number (%) of patients with maximum intensity grade ≥ 3 TEAEs related to W_pro1 by system organ class and preferred term	Safety set	Yes

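### A missing cemiplimab causality item makes an AE cemiplimab-related and IMP-related even in patients who never received cemiplimab

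*SAP*

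**What the plan says.** SAP 8.9.3 gives each compound a default for a missing causality entry. For W_pro1: "If the item is missing, the AE will be considered as related to W_pro1". For cemiplimab: "If the item is missing, the AE will be considered as related to cemiplimab". Neither sentence carries a condition on arm, exposure or timing. The relationship to trial drug overall is then defined as: "AEs related to IMP are AEs related to either W_pro1 or cemiplimab (or both".

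These derivations feed tables by relationship. SAP 8.9.3 lists, among others, "TEAEs related to Cemiplimab by System Organ Class and Preferred Term", with further cemiplimab-related and IMP-related versions for Grade 3 or higher, serious and fatal events. The table list in SAP 11.1.1 assigns "Number (%) of patients with TEAEs related to Cemiplimab by system organ class and preferred term" (Table 14.3.1.5) to the safety set.

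SAP 7.1 defines that set by receipt of either drug: "The safety set is defined as all patients who have received IMP (i.e., at least 1 dose of W_pro1 and/or cemiplimab". SAP 8.9 adds: "All safety analyses will be based on the safety set and will be summarized by treatment groups". Patients given only W_pro1 are therefore in these tables. SAP 13.4 also defines pooled monotherapy columns for the AE analyses.

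On the recording side, the protocol (Appendix 3, Assessment of Causality) says: "It is sufficient to document the causality in the source data and eCRF as", followed by two entries, Related and Not related.

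**The concern.** Treating a missing causality entry as related is a reasonable cautious default for a drug the patient has received. For a drug never given, or first given after the event, it is an impossible attribution. Part 1 and Arm 3 receive no cemiplimab. Arm 1B receives it only if the patient takes up the option after progression.

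The protocol text names only two causality entries. Not applicable is offered under action taken with trial treatment, but not under causality. A site completing the form for a patient not on cemiplimab could plausibly leave the item empty.

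The either-compound definition then carries the error further. An AE that the investigator judged unrelated to W_pro1, the only investigational drug the patient had, would be reported as related to IMP. TEAEs by relationship are part of the primary safety endpoint (SAP 8.9.1), and the error runs in one direction only: it adds related events to the monotherapy columns.

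**Working it through.** The plan states no figure that depends on this rule, so there is nothing to reproduce. The check has two parts: whether any other text limits the rule, and what the rule does algebraically.

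**Is the rule limited elsewhere?**

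- SAP 8.3 says missing data are not imputed unless specified otherwise. SAP 8.9.3 is such a specification, so the general rule gives way.
- SAP 8.9.2 deals with patients who did not receive a compound, setting their exposure parameters for it to 0. There is no counterpart for causality.
- The SAP restricts AE outputs by arm where it means to: surgery-related TEAEs are marked for Arms 2 and 3, and DLTs for Part 1. The cemiplimab-related outputs carry no such mark.
- SAP 13.4 applies the AE analyses to all five treatment groups and to pooled groups, including Arm 1B with Arm 3, and Part 1 with both.

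No passage restricts the default to patients given cemiplimab.

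**What the rule does.** Consider AEs in patients not exposed to cemiplimab. Let r be the share counted as related to W_pro1, and b the share with a blank cemiplimab item. Assume that b is independent of the W_pro1 entry and that every completed cemiplimab item reads Not related. Then:

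- share cemiplimab-related = b
- share IMP-related = r + (1 − r) × b

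The documents give neither r nor b. Taking r = 60% purely as an illustration:

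| b | Cemiplimab-related | IMP-related |
|---|---|---|
| 0% | 0% | 0.60 + 0.40 × 0 = 60% |
| 50% | 50% | 0.60 + 0.40 × 0.5 = 80% |
| 100% | 100% | 0.60 + 0.40 × 1 = 100% |

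For any r, the IMP-related share runs from r (no blanks) to 100% (all blank). With an exposure condition on the default, the cemiplimab-related share is 0 and the IMP-related share is r, whatever b is.

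These are shares of events. The tables also count patients, and there a single blank item is enough to move a patient into a related row.

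**What is untouched.** W_pro1-related rows and tables use only the W_pro1 item. All monotherapy patients are assigned W_pro1, so its own missing-item default raises no comparable problem. DLTs rest on relationship to BNT112 (Protocol 6.6.1.1), so the cemiplimab item plays no part.

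**The case against.** The strongest reply is that the effect hangs on a form nobody outside the sponsor can see. The protocol obliges the investigator to assess relationship for every AE, Not related is a correct entry for a drug never given, and the eCRF may hide the item or offer a further option. The table layouts sit in a separate mock document that might suppress these cells. All of that stands as a limit on size. It does not rescue the rule: the SAP provides for blanks, so it should say what a blank means in an unexposed patient.

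The reply also narrows the consequences. A reader might infer any of four stronger conclusions, none of which the documents support:

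- *The rule widens the TEAE window, because late AEs count if related to IMP.* SAP 8.9.3 requires that the investigator assessed the late event as related. A programmed default is not clearly such an assessment.
- *The planned sizes of Part 1, Arm 1B and Arm 3 give the number affected.* SAP 5 and 8.7.6 report that mCRPC enrollment was stopped after the interim analysis. The final Arm 1B number is not given.
- *Spurious fatal and serious cemiplimab-related events are likely.* Protocol Appendix 3 requires a causality assessment before an SAE is first sent to the sponsor, so blanks are least expected there. That text does not settle how the cemiplimab item is filled for patients not given the drug.
- *The monotherapy versus combination safety picture is lost.* The separate W_pro1-related tables, including Grade 3 or higher, serious and fatal events, still give a sound drug-related count for monotherapy patients. SAP 4 plans no formal comparison between arms.

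**Conclusion.** The point holds as a defect in a stated rule; misclassification has not been shown to have occurred. As written, SAP 8.9.3 turns any blank cemiplimab item in a patient without cemiplimab exposure into a cemiplimab-related and IMP-related AE, and nothing else in either document stops it. The rows at risk are the cemiplimab-related and IMP-related ones in Part 1, Arm 3, Arm 1B (for AEs before or without the switch) and the pooled columns that contain these groups.

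The size lies between nil, if sites always enter Not related, and all AEs in unexposed patients, if the item is always blank. Where it falls depends on eCRF behavior that the documents do not show. Because the rule bears on a primary endpoint and is trivial to correct, it should be corrected.

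**What to change.** Amend SAP 8.9.3 along these lines: *a missing cemiplimab causality item is counted as related to cemiplimab only where the patient had received at least one dose of cemiplimab on or before the date the AE began or worsened; in every other case the AE is counted as not related to cemiplimab.* Derive the relationship to IMP from that result.

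Three details need care:

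- Keep the missing-means-related default for patients who have received cemiplimab. Including worsening matters for switched Arm 1B patients: an AE that began on W_pro1 and worsened on cemiplimab should keep the cautious default. Protocol Appendix 3 already has the date of each change in intensity recorded.
- Keep the SAP's deliberate double counting of AEs that start after the first cemiplimab dose but within 30 days of the last W_pro1 dose. These can be genuine cemiplimab-related events under Arm 1B, so the Arm 1B rows should not be blanked.
- Show cemiplimab-related rows as not applicable only for the groups never given the drug, Part 1 and Arm 3.

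The cost is a sentence in the SAP, a condition in the AE derivation program and a table convention. It is also worth counting blank cemiplimab items by arm now. SAP 11.1.1 flagged the IMP-related TEAE table (14.3.1.3) and the Grade 3 or higher and serious cemiplimab-related tables (14.3.1.9 and 14.3.1.15) for the interim analysis, so those outputs should be checked against the same count.

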8.9.4 Laboratory assessments

Clinical laboratory data to be summarized include hematology, blood chemistry, coagulation, thyroid hormones and urinalysis. The clinical laboratory parameters to be assessed are listed in [Table 8-2](#) and the scheduled time points for assessment are presented in the SoA (see Section [13.6](#)).

All laboratory parameters, except serology assessments, are reported in the clinical database using local safety laboratories. Measurements and corresponding Low and High ranges will be converted into Standard International (SI) units. Values outside the normal ranges are classified as “Not clinically significant” or “Clinically significant” by the investigator.

Serology parameters are analyzed by a central laboratory.

For the derivation of the minimum post-baseline measurement / maximum post-baseline measurement / or worst post-baseline toxicity CTC grades, measurements collected at unscheduled visits will be considered.

The End of Study measurement is defined as last available safety assessment, either at Safety FU D30 or Safety FU D90 Visit (whichever occurs later) or last available safety assessment in case of early trial discontinuation or death. Measurements after switch to cemiplimab monotherapy will not be considered in the derivation of the End of Study measurement.

Clinical laboratory parameters at each scheduled visit and change from baseline to each post-baseline time point will be summarized using descriptive summary statistics for each parameter by treatment group.

The number and percentage of patients reporting markedly abnormal clinical laboratory values as reported by the investigator at any point on the trial will be summarized for each parameter by visit and treatment group using the following categories: Clinically significant low, Low, Normal, High, Clinically significant high.

Shift tables from baseline to Minimum Post-baseline / Maximum Post-baseline and to End of Study measurement with respect to reference range values (Clinically significant low, Low, Normal, High, Clinically significant high) will be generated for each parameter by treatment group.

Clinical laboratory results will be classified according to of NCI CTCAE v5.0. Laboratory results not corresponding to a NCI CTCAE term will not be graded. CTC grades for the respective parameters will be reported using the following categories: Grade 0, Grade 1, Grade 2, Grade 3, Grade 4 by visit and treatment group. Shift tables from baseline to worst post-baseline toxicity grade and to End of Study measurement will be provided for each laboratory parameter by treatment group.

A list of laboratory parameters to be analyzed by CTC grades is available in Section [13.6](#).

Urinalysis, dipstick results will be reported only by number of patients and percentage for each parameter by visit and treatment group.

Microscopic urinalysis parameters (where available), serology parameters and circulating tumor cells will be listed only.

All clinical laboratory data will also be presented in the data listings. Abnormal clinical laboratory values and clinically significant values as reported by the investigator will be flagged in the listing.

Table 8-2: Local Safety Laboratory Tests (Blood and Urine) - Overview

Parameters (by group)
Hematology: hemoglobin, hematocrit, red blood cell count (RBC), white blood cell count (WBC) and differential (neutrophils, lymphocytes, monocytes, eosinophils, basophils), platelet count
Coagulation: international normalized ratio (INR), activated partial thromboplastin time, fibrinogen
Blood chemistry: alkaline phosphatase (ALP), creatinine, ferritin, C-reactive protein (CRP), albumin, alanine aminotransferase (ALT), amylase, aspartate aminotransferase (AST), gamma glutamyl transpeptidase (GGT), total bilirubin, blood urea nitrogen (BUN), glucose, lipase, sodium, potassium, calcium
Thyroid Hormones (only collected for Arm 1A and Arm 2) thyroid function (thyroid stimulating hormone [TSH], free thyroxine [fT4], free triiodothyronine [fT3] and total triiodothyronine [T3])
Urinalysis: Dipstick: specific gravity, pH, glucose, protein, ketones, blood Microscopic urinalysis: If warranted by dipstick results, urine sediment will be microscopically examined for presence of red blood cells, white blood cells, casts, crystals, epithelial cells, and bacteria
Circulating tumor cells (optional)
Serology (provided by a central laboratory): Hepatitis B Virus Core Antibody, Hepatitis B Virus Core IgM Antibody, Hepatitis B Virus Surface Antigen, Hepatitis B Virus Surface Antibody, Hepatitis C Virus Antibody, HIV-1/2 Antibody + HIV-1 p24 Antigen The following serology parameters will be provided only in case of positive findings in the normal serology tests above: Hepatitis C Virus RNA, Hepatitis B Virus Surface Antibody (quantitative), Hepatitis B Virus e Antigen, Hepatitis B Virus DNA, HIV-1 p24 Antigen, HIV-1/2 Antibody, HIV 1 (Blot), HIV 2 (Blot), HIV-1 RNA

